6.4. Multicenter Studies

This study will be conducted by multiple investigators at multiple sites internationally. No estimation of interaction effects or adjustments by country or region will be performed due to the limited sample size in each treatment group and nature of the study.

6.5. Multiple Comparisons/Multiplicity

No multiplicity adjustments will be made due to the nature of the study.

6.6. Patient Disposition

Screen failures and reason for screen failure will be summarized. The treatment disposition and study disposition will be summarized for the modified intent-to-treat (mITT) population. Disposition summaries will be by weight/treatment dose group and overall. Summaries will also include reason for discontinuation from the study tabulated by weight/treatment group for all patients.

Additionally, a listing of all patients who are enrolled and received at least one dose of miri (ie, the mITT population) and discontinued from study treatment during any period from the study

will be provided, and the timing of discontinuing the study will be reported. If known, a reason for their discontinuation will be given.

6.7. Patient Characteristics

Patient demographic variables and baseline characteristics will be summarized by weight/treatment dose groups and overall for the mITT populations with the baseline values. The continuous variables will be summarized using descriptive statistics (N, mean, SD, minimum, Q1, median, Q3, and maximum) and the categorical variables will be summarized using frequency counts and percentages. No inferential analysis for the comparability of baseline covariates across groups will be performed. By-patient listings of basic demographic characteristics (ie, age, sex, race, racial subgroup, ethnicity, country, body weight) will be provided.

 Table AMBU.6.3.
 Patient Characteristics (and Variables for Analysis)

Variable	Continuous Summary	Categorical Summary
Demographic Characteristics		
Agea	Yes	2 - < 8 years, $8 - < 12$ years, $12 - < 18$ years
Sex	No	Male, Female
Ethnicity	No	Hispanic/Latino, Non-Hispanic/Non-Latino
Race	No	American Indian/Alaska Native, Asian, Black/African American, Native Hawaiian or other Pacific Islander, White, or Multiple
Geographic Region	No	By Country (listed in other documents)
Height (cm)	Yes	None
Weight (kg)	Yes	>40 kg, ≤40 kg and >20 kg, ≤20 kg
BMI ^b	Yes	Underweight ($<18.5 \text{ kg/m}^2$), Normal ($\ge18.5 \text{ and } <25 \text{ kg/m}^2$), Overweight ($\ge25 \text{ and } <30 \text{ kg/m}^2$), Obese ($\ge30 \text{ and } <40 \text{ kg/m}^2$), Extreme obese ($\ge40 \text{ kg/m}^2$)
Tobacco/Nicotine Replacement use (for ages ≥12)	No	Never, Current, Former
Alcohol use (for ages ≥12)	No	Never, Current, Former
Caffeine use (for ages ≥12)	No	Never, Current, Former
Prior UC Therapy		
Prior biologic ^c exposure	No	Ever, Never
Prior biologic ^c failure ^d	No	Failed, Not failed
Prior biologic ^c failure ^d excluding JAK ^g inhibitors	No	Failed, Not failed
Inadequate response or loss of response to a biologic ^c	No	Ever, Never
Inadequate response to a biologic ^c	No	Ever, Never
Loss of response to a biologic ^c	No	Ever, Never
Intolerance to a biologic ^c	No	Ever, Never
Number of prior biologics used ^c	No	0, 1, 2, >2
Number of failed ^d biologics ^c	No	0, 1, 2, >2
Prior biologic failure ^d and prior biologic exposures	No	Not exposed, Exposed but not failed, Exposed and failed at least one
Prior anti-TNFe failured	No	Failed, Not failed

Variable	Continuous Summary	Categorical Summary
Number of failed ^d (unique) prior anti-TNFs ^e	No	0,1, 2, >2
Prior anti-integrinf failured	No	Ever, Never
Prior failured of a JAKg inhibitor	No	Ever, Never
Prior corticosteroid failured	No	Ever, Never
Prior immunomodulator	NI	·
failure ^{d, h}	No	Ever, Never
Baseline UC Therapies		
Baseline corticosteroid useh	No	Yes, No
Baseline prednisone equivalent dose	Yes	None
Budesonide MMX	No	Yes, No
Baseline immunomodulator use ^h	No	Yes, No
Baseline corticosteroid and immunomodulator useh	No	Corticosteroid only, Immunomodulator, Neither, Both
Baseline use of oral aminosalicilatesi	No	Yes, No
Baseline use of methotrexateh	No	Yes, No
Baseline use of thiopurineh	No	Yes, No
Baseline Disease Characteristics		
Duration of UCi	Yes	<1 year, ≥ 1 to <3 years, ≥ 3 year to <7 years, ≥ 7 years
Age at Diagnosis of UCk	Yes	$<6, \ge 6$ to <10 year, ≥ 10 to <17 years
Historical Disease Severity	No	Ever Severe, Never Severe
Baseline Disease Extent	No	Ulcerative proctitis (rectum), Left-sided (descending or sigmoid colon), Extensive (transverse colon), Pancolitis (cecum or ascending colon)
Baseline Fecal Calprotectin	Yes	≤250 μg/g, >250 μg/g
Baseline C-reactive Protein (CRP)	Yes	≤6 mg/L, >6 mg/L
Baseline Modified Mayo Score	Yes	Moderate (4-6), Severe (7-9)
Baseline Total Mayo Score	Yes	Moderate (6-9), Severe (10-12)
Baseline Partial Mayo Score	Yes	None
Baseline Endoscopic Mayo Subcore	No	Possible values of 4-point scale in Table AMBU.6.4
Baseline Stool Frequency Mayo Subscore	No	Possible values of 4-point scale in Table AMBU.6.4
Baseline Rectal Bleeding Mayo Subscore	No	Possible values of 4-point scale in Table AMBU.6.4
Baseline PGA Mayo Subscore	No	Possible values of 4-point scale in Table AMBU.6.4
Baseline PUCAI	No	Severe (65-85), Moderate (35-60), Mild (10-30), None (<10)
CCI		
Baseline Abdominal Pain NRS	Yes	<4,≥4
Baseline Patient's Global Rating of Severity (PGRS)	Yes	None
Baseline Nocturnal Stool	Yes	Yes (≥1), No (0)
Baseline Bristol Stool Scale	No	Not Loose Stool (1 – 3), Loose Stool (4-5)

Abbreviations: ATC = Anatomical Therapeutic Chemical; BMI = body mass index; DOB = date of birth; eCRF = electronic case report form; JAK = Janus kinase; NRS = numeric rating scale; PGA = Physician's Global Assessment; PUCAI = Pediatric Ulcerative Colitis Activity Index; TNF = tumor necrosis factor; UC = ulcerative colitis

- ^a Age in years will be calculated as length of the time interval from the DOB to the informed consent date.
- b Body mass index (BMI) will be calculated as: $BMI(kg/m^2) = Weight(kg)/(Height(m))^2$.
- ^c Biologic systemic therapies include: adalimumab, adalimumab biosimilar, alemtuzumab, brazikumab, certolizumab, golimumab, guselkumab, infliximab, infliximab biosimilar, interferon therapy, other TNF biosimilar, risankizumab, rituximab, tildrakizumab, ustekinumab, vedolizumab, visilizumab, tofacitinib, and other JAK inhibitors. For the purpose of counting the number of prior biologics, adalimumab and adalimumab biosimilar will be counted as one biologic
- d Failure defined as reasons for prior treatment discontinuation are: loss of response, inadequate response or intolerance to medication.
- e Anti-TNF alpha biologics include: infliximab, infliximab biosimilar, adalimumab, adalimumab biosimilar, golimumab, certolizumab pegol.
- f Possible anti-integrin treatments include vedolizumab.
- g Options on the prior medications eCRF for JAK inhibitors include: tofacitinib and other JAK inhibitor.
- h ATC codes for immunomodulators including methotrexate and thiopurines are listed in the compound level safety standards.
- i Aminosalicilates will be defined using ATC code A07EC (all members).
- j Length of the interval from the date of UC diagnosis to the date of informed consent.
- k Age at diagnosis in years will be calculated as the time interval from the DOB to the date of UC diagnosis.

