6.1. Inclusion Criteria

Patients are eligible to be included in the study only if they meet all of the following criteria within the screening period, which is CCI [REDACTED], unless otherwise specified below:

Informed Consent

- [1] Have given assent (if appropriate) with parent/legal guardian signed informed consent approved by the ethical review board (ERB) governing the site.

Patient Characteristics

[figure not shown]
- [2] Male or female patients weighing >10 kg AND ≥ 2 and <18 years of age at the time of informed consent.

[2a]

CCI [REDACTED]

[2b]

CCI [REDACTED]

[3] Both the parent or legal representative and child (if capable) must agree to comply with the requirements of the protocol.

[4] CCI [Redacted]

Type of Patient and Disease Characteristics

[5] Have an established diagnosis of UC of ≥ 3 months in duration before baseline, CCI [Redacted]

[6] Have moderately to severely active UC as defined by a CCI [Redacted] within CCI [Redacted] before first dose of study treatment (baseline).

[7] Have evidence of UC extending proximal to the rectum CCI [Redacted]

Prior Medication Failure Criteria

[8] Patients must have an inadequate response to, loss of response to, or intolerance to at least 1 of the medications described in Criteria [8a] OR [8b]. **Documentation of dose, frequency, route of administration, and duration of the prior failed treatment is required.**

[8a] **Biologic-naive patients:** Patients who have an inadequate response to, loss of response to, or are intolerant to at least 1 of the following medications:

- Corticosteroids
 - Corticosteroid-refractory colitis, defined as signs and/or symptoms of active UC despite a CCI [REDACTED]

CCI [REDACTED]

CCI [REDACTED]

- Immunomodulators:
 - Signs and/or symptoms of persistently active disease despite at least 3 months' treatment with 1 of the following:

- Oral AZA CCI [REDACTED] or 6-MP CCI [REDACTED], or

CCI [REDACTED]

- History of intolerance to at least 1 immunomodulator CCI [REDACTED]

Discontinuation despite clinical benefit does not qualify as having failed or being intolerant to UC non-biologic therapy.

[8b] **Biologic/JAK inhibitor-experienced patients:** Patients who have an inadequate response to, CCI [REDACTED] to biologic therapy for UC (such as anti-TNF antibodies or anti CCI [REDACTED] antibodies) and/or to JAK inhibitors (such as tofacitinib), as described below.

Investigators must document an adequate trial of the medication.

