5.1. Summary of Study Design

Study AMBU is a multicenter, open-label study designed to evaluate the safety, pharmacokinetics (PK), pharmacodynamics (PD), and clinical response of mirikizumab in pediatric patients (ages 2 to <18 years old) and to provide data for dose confirmation for Phase 3. The study population includes pediatric patients with moderately to severely active ulcerative colitis (UC), who have an inadequate response to, loss of response to, or are intolerant to nonbiologic therapy for UC (biologic-naive), and/or those who have been exposed to at least 1 biologic and/or Janus kinase inhibitor therapy for UC (biologic/ Janus kinase inhibitor-experienced).

Patients weighing >40 kg will receive a mirikizumab induction dose of 300 mg via intravenous (IV) infusion and patients weighing ≤40 kg will receive 5 or 10 mg/kg via IV infusion at Weeks 0, 4, and 8. Patients who have met the clinical response criteria at Week 12 will receive subcutaneous (SC) maintenance doses of 200 mg (weight >40 kg), or 100 mg (weight >20 kg to ≤40 kg), or 50 mg (weight ≤20 kg) every 4 weeks from Weeks 12 to 48. Patients who have not achieved clinical response at Week 12 may receive extended induction at the next higher available dose, or will be discontinued. In cases where there is no higher dose, patients may receive extended induction dosing at the current dose. Approximately 60 patients with moderately to severely active UC will be screened to enroll approximately 30 patients.

Figure AMBU.5.1 illustrates the study design.

Figure AMBU.5.1. Illustration of study design for clinical protocol I6T-MC-AMBU.

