5.2. Determination of Sample Size

Lilly plans to enroll approximately 30 patients into Study AMBU, to achieve at least 25 evaluable patients with respect to evaluating mirikizumab PK. The enrollment target includes approximately 10 patients in the >40 kg category and approximately 20 patients in the \le 40 kg category.

This sample size is considered adequate to evaluate the PK of mirikizumab treatment in pediatric patients.

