		response	reduction in baseline PUCAI score of ≥20	missing.
		1	points.	8

Measure	Description	Variable	Derivation / Comment	Definition of Missing
	CCI			
Histo-Endo	Combined histology and endoscopic endpoints.	Histologic-endoscopic mucosal improvement Histologic-endoscopic	Histologic improvement and endoscopic remission. Defined as achieving both histologic	Missing if any component of the definition is missing. Missing if any component of the
		mucosal remission	remission and endoscopic remission	definition is missing.
CRP	C-reactive protein (CRP) is a biomarker of inflammation.	CRP	Lab value. May be transformed if needed.	Single lab value. Missing if missing.
Fecal calprotectin	Fecal calprotectin is used as a biomarker of intestinal inflammation in clinical practice.	Fecal calprotectin	Lab value. May be transformed if needed.	Single lab value. Missing if missing.
Growth and Pubertal Assessments	Occipital head circumference	Head circumference	Occipital head circumference measurements will be performed on patients less than 3 years of age at baseline. Measurements will be taken at baseline and then approximately Q12W thereafter, until the patient reaches the age of 3 years.	Data will be missing for patients who are 3 years or older at entry. Missing if missing.
	Change from baseline in height (cm)	Height CFB	Change from baseline in height (cm) at all study visits. Height is measured 3 times at all visits, height at each visit is calculated	Missing if baseline height or height at visit is missing.

Measure	Description	Variable	Derivation / Comment	Definition of Missing
			using the average of the 3 measurements.	
	Change from baseline in weight (kg)	Weight CFB	Change from baseline in weight (kg) at all study visits.	Missing if baseline weight or weight at visit is missing.
	Height Z-score and percentile by sex and age will be calculated using the CDC growth data shown at: https://www.cdc.gov/nccdphp/dnpao/growthcharts/resources/sas.htm	Height Z-score Height Percentile	Observed height z-score and percentile by sex and age	Missing if height at visit is missing.
	This approach uses a Box-Cox transformation to calculate the height z-score and percentile of the normal distribution for the corresponding age and sex.			
	Height Percentile Change from Baseline	Height Percentile CFB	Change from Baseline is calculated as Present height percentile – Baseline height percentile	Missing if baseline height or height at visit is missing.

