	Weight Z-score and percentile by sex and age will be calculated using the CDC growth data shown at: https://www.cdc.gov/nccdphp/dnpao/growthcharts/resources/sas.htm This approach uses a Box-Cox	Weight Z-score Weight Percentile	Observed weight z-score and percentile by sex and age	Missing if weight at visit is missing.
	transformation to calculate the weight z-score and percentile of the normal distribution for the corresponding age and sex.			
	Weight Percentile Change from Baseline	Weight Percentile CFB	Change from Baseline is calculated as Present weight percentile – Baseline weight percentile	Missing if baseline weight or weight at visit is missing.
	Observed height velocity by gender and age group. Age groups for which	Height velocity	Observed height velocity by gender and age group will be calculated at baseline	Data will be missing if either present height or previous height

Measure	Description	Variable	Derivation / Comment	Definition of Missing
	this will be summarized are 2 to <8, 8 to <12, and 12 to <18.		according to the following formula: (Present Height [cm] - Previous Height [cm])/Interval (months) Between Measurements × 12	is missing.
Assessment of Puberty	Total testosterone levels will be collected from male patients ≥9 years of age. Estradiol levels will be collected from female patients ≥9 years of age, until the female begins menstruating. If the patient is 9 years of age and has already begun menstruation, estradiol levels will not be required.	Hormone level	Total testosterone levels for male patients ≥9 years of age and estradiol levels for female patients ≥9 years of age, until the female begins menstruating.	Missing if patients are less than 9 years old or if date of onset of menstruation for females if exists. Missing if missing.
EIMs	Extraintestinal manifestations (EIMs) are collected using the	Baseline EIMs	EIMs ongoing at first dose of study treatment.	No Imputation.

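### Baseline BMI is categorised with fixed limits that ignore age and sex in patients aged 2 to <18 years, so the category counts would largely reflect age and body size

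*SAP*

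**What the plan says.** SAP Section 6.7, Table AMBU.6.3, has a BMI row among the demographic characteristics. It is summarised both continuously and in five classes. The lowest class is "Underweight ($<18.5" kg/m²), followed by Normal (18.5 to <25), Overweight (25 to <30), Obese (30 to <40) and "Extreme obese" (40 or more). The footnote beginning "Body mass index (BMI) will be calculated as" gives only weight in kg divided by the square of height in metres. It contains no adjustment for age or sex.

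The SAP (Section 5.1) describes the study as evaluating "clinical response of mirikizumab in pediatric patients (ages 2 to <18 years old"), and the protocol (Section 6.1) admits "Male or female patients weighing >10 kg AND ≥ 2 and <18 years of age". The planned enrolment in SAP Section 5.2 is "approximately 10 patients in the >40 kg category and approximately 20 patients" at ≤40 kg. The table is presented by weight/treatment dose group and overall, and the groupings in Table AMBU.6.2 split at 40 kg.

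For other body measurements the plan does take account of age. Table AMBU.6.4 states that "Height Z-score and percentile by sex and age will be calculated using the CDC growth data shown at" a cited web resource, and likewise "Weight Z-score and percentile by sex and age will be calculated using the CDC growth data". Protocol Section 9.1.6.2 defines age- and sex-specific z-scores for height velocity, and SAP Table AMBU.6.7 sets blood pressure and pulse limits by age band. Neither document gives a BMI-for-age percentile, z-score or category.

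**The concern.** Expected BMI changes over childhood. A single limit of 18.5 kg/m² applied from age 2 to just under 18 therefore does not carry the same meaning across the age range. In small children the label Underweight can be triggered by ordinary proportions rather than by poor nutrition. At the other end, the Overweight and Obese classes are very hard for a small child to reach.

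What is at stake is the accuracy of one printed row. Growth and weight are of direct interest in paediatric ulcerative colitis, and the plan has secondary objectives on both, so readers will look at the baseline nutritional description. They would see an Underweight count that is high in the ≤40 kg columns and lower in the >40 kg column, and could take it for a nutritional difference. The same report could place a child at an unremarkable CDC weight percentile and also count that child as Underweight. Demographics are part of the interim analysis in SAP Section 6.16.2, so the row may appear there too. SAP Section 6.14 also leaves room for subgroups on any baseline characteristic, and a subgroup by these BMI classes would act mainly as a subgroup by age and weight.

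**Working it through.** The plan states no figure of its own to reproduce. The check has two parts: one uses only the SAP's formula and limits, and the other needs assumptions that are not in the documents.

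**Part 1: from the SAP alone.** BMI = weight / height² (Table AMBU.6.3 footnote). A child falls below a limit L when height exceeds √(weight / L).

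| Weight | Underweight if taller than √(weight/18.5) | Overweight or above only if no taller than √(weight/25) |
|---|---|---|
| 15 kg | √0.811 = 0.90 m | √0.600 = 0.77 m |
| 20 kg | √1.081 = 1.04 m | √0.800 = 0.89 m |
| 30 kg | √1.622 = 1.27 m | √1.200 = 1.10 m |
| 40 kg | √2.162 = 1.47 m | √1.600 = 1.26 m |

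These heights follow from the plan and rest on no outside figure.

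**Part 2: with stated assumptions.** To say how often the label would apply, one needs typical heights or a BMI distribution by age. The documents give neither, so the following are assumptions.

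*Assumed height ranges, with BMI = weight / height²:*

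| Weight | Assumed height | BMI range | Position against 18.5 |
|---|---|---|---|
| 15 kg | 0.95–1.05 m | 13.6–16.6 | all below |
| 20 kg | 1.08–1.20 m | 13.9–17.1 | all below |
| 25 kg | 1.20–1.32 m | 14.3–17.4 | all below |
| 30 kg | 1.30–1.42 m | 14.9–17.8 | all below |
| 40 kg | 1.42–1.58 m | 16.0–19.8 | straddles |

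*Assumed normal BMI distribution, with share classed Underweight = Φ((18.5 − mean)/SD):*

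- Mean 15, SD 1.5: Φ(2.33) = 99%
- Mean 15, SD 3: Φ(1.17) = 88%
- Mean 17, SD 1.5: Φ(1.00) = 84%
- Mean 17, SD 3: Φ(0.50) = 69%
- Mean 20, SD 1.5: Φ(−1.00) = 16%
- Mean 20, SD 3: Φ(−0.50) = 31%

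Means of 15 to 17 stand for young children and a mean of 20 for older adolescents. The range is 69% to 99% for the former and 16% to 31% for the latter.

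**Where it falls in the table.** About 20 of the 30 planned patients (20/30 = 67%) are at ≤40 kg, where the label applies most readily. The 69% to 99% range should not be applied to all 20, because the effect weakens as weight approaches 40 kg.

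**The case against.** The best answer for the plan is that little depends on this row. BMI is also reported continuously by group, as are age, height and weight. Age and weight are listed by patient. Height and weight percentiles have to be derived in any case to obtain their planned change from baseline, although Table AMBU.6.5 lists only the change. So body size is not described by the contested classes alone. This stands, and it limits the importance of the point. It does not correct the Underweight count that would be printed.

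Three stronger readings are tempting and are not supported.

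- **Dosing is affected.** A reader might infer this because the trial doses by weight. In both documents dose and group depend on body weight in kg, and no rule uses BMI or a BMI class.
- **A treatment comparison is confounded.** SAP Section 6.2 plans no treatment comparisons, and Section 6.7 rules out inferential comparison of baseline variables. The columns are defined by weight, so age, height and continuous BMI will also differ between them by design. The 5 and 10 mg/kg groups are both ≤40 kg, so the weight cut-off does not separate those two.
- **The documents show that many normally built children would be misclassified.** They show the heights at which the label applies. How many children exceed those heights depends on the assumptions above. Nor does the SAP call its limits adult ones; what can be shown is that they do not vary with age or sex.

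It is also fair to object that the documents cite the CDC resource for height and weight only and do not say whether it yields BMI-for-age. The proposed change allows for that.

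**Conclusion.** The point holds as a minor one. Table AMBU.6.3 applies one age- and sex-invariant BMI scale to patients aged 2 to <18 years, and nothing elsewhere in the plan corrects it. The height thresholds follow directly from the SAP's formula. The expected frequencies (69% to 99% in young children, 16% to 31% in older adolescents) rest on the assumed BMI means and SDs. The direction does not depend on a particular choice within the ranges tried: for 15 to 30 kg every assumed height gives a BMI below 18.5, while at 40 kg the result is mixed. The counts would therefore mainly track age and body size, and would differ between the ≤40 kg and >40 kg columns for that reason.

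The consequence is confined to a descriptive baseline row, wherever it is produced, and to any optional BMI subgroup. The primary PK analysis is delegated to a separate PK/PD plan, and neither document links the BMI classes to it, to dosing or to any efficacy endpoint.

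**What to change.** In Table AMBU.6.3, replace the five fixed classes with BMI-for-age-and-sex percentile or z-score categories, using the CDC growth reference the SAP already cites for height and weight, and state the category limits in the SAP. If that resource does not provide BMI, delete the categorical entry and keep the continuous summary. If a BMI subgroup is ever run under SAP Section 6.14, it should use the age- and sex-standardised measure.

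The cost is one table row and its footnote. Age, sex, height and weight are already collected, so no new data are needed. No corrected count can be given here because the reference tables are not in the documents.

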Remission rates in pediatric UC have been evaluated in pediatric clinical trials and retrospective reviews, and these evaluations have indicated that 29% to 50% of children with moderate-to-severe disease achieved steroid-free remission at 1 year (Hyams et al. 2006, 2011, 2012; Zeisler et al. 2013). Current treatments for pediatric patients with UC have significant limitations with respect to efficacy, safety, and tolerability. In addition, many treatments require close monitoring for adverse effects, which increases undue burden on the child and family. Thus, there is a substantial unmet need for the development and approval of efficacious, safe, and well-tolerated therapies for children and adolescents with UC.

To date, the anti-tumor necrosis factor (TNF) antibody, infliximab, is the only biologic therapy approved to treat UC in pediatric patients. Although anti-TNF therapy has improved disease course in UC, lack of efficacy and loss of response continue to be a concern in this patient population (Hyams et al. 2012).

The safety profile of current therapies, including infliximab, may also limit their use in some patients. Treatment with infliximab is associated with an increased risk for serious infections leading to hospitalization or death, including tuberculosis (TB), bacterial sepsis, invasive fungal infection (for example, histoplasmosis), and infections caused by other opportunistic pathogens. Lymphoma and other malignancies, some fatal such as hepatosplenic T-cell lymphoma, have also been reported in children and adolescent patients treated with TNF blockers, particularly when these agents are used in combination with immunomodulators. In addition, the development of anti-TNF antibodies is associated with acute infusion reactions, delayed hypersensitivity reactions, decreased serum drug levels, and loss of response (Miele et al. 2004), leading to potentially significant safety and efficacy concerns.

While treatment with corticosteroids is effective in inducing clinical response or remission in the majority of patients, almost 50% of patients develop corticosteroid dependence and require additional medication to successfully discontinue corticosteroids (Jakobsen et al. 2011b). Corticosteroids are not effective in maintaining remission in patients with UC, and long-term corticosteroid therapy is limited by the potential for significant adverse effects. Although

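### SAP Table AMBU.6.3 merges adalimumab with its biosimilar but has no such rule for infliximab, so read literally one molecule can count as two prior biologics (minor)

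*SAP*

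**What the plan says.** SAP Section 6.7, Table AMBU.6.3, summarises prior therapy by weight/treatment dose group and overall. Three rows are counts with categories 0, 1, 2 and >2:

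- biologics used ("Number of prior biologics used"), governed by footnote c;
- biologics failed, governed by footnotes c and d;
- failed anti-TNFs, labelled as unique, governed by footnotes d and e.

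Footnote c lists the products that count as biologics. Both adalimumab products appear in it, and so do both infliximab products; part of the list reads "golimumab, guselkumab, infliximab, infliximab biosimilar, interferon therapy, other TNF biosimilar". The only counting rule follows that list and says that, when prior biologics are counted, "adalimumab and adalimumab biosimilar will be counted as one biologic".

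Footnote d defines failure by the reason for stopping: loss of response, inadequate response or intolerance. Footnote e sets out the anti-TNF products: "Anti-TNF alpha biologics include: infliximab, infliximab biosimilar, adalimumab, adalimumab biosimilar, golimumab, certolizumab pegol". It has no merge rule for either pair, and the SAP does not define unique.

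Protocol Section 3.2.2 says that infliximab "is the only biologic therapy approved to treat UC in pediatric patients".

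**The concern.** The footnote treats two parallel situations differently. Originator and biosimilar adalimumab are one molecule and count once. Originator and biosimilar infliximab are also one molecule, listed in the same footnote, and have no such rule. A programmer who follows the text literally would count infliximab twice for a child who received both products.

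These rows tell the reader how heavily pretreated the children were. Counting one molecule twice overstates that, and it does so for children treated with infliximab but not for those treated with adalimumab. Infliximab is also the one biologic that the protocol describes as approved for this population, so it is an awkward product to leave out.

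**Working it through.** The plan states no figure to reproduce, so the check applies the rule as written to example histories.

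**Inputs.** The product list and merge rule come from footnote c, the definition of failure from footnote d, and the categories from Table AMBU.6.3. SAP Section 5.2 gives the planned sizes: about 10 children above 40 kg and about 20 at or below 40 kg, so 10 + 20 = 30.

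**Rule.** Count = number of distinct listed products left after the stated merges. The count is then placed in 0, 1, 2 or >2.

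**Biologics used.**

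| Products received | As written | With infliximab also merged |
|---|---|---|
| adalimumab + its biosimilar | 1 | 1 |
| infliximab + its biosimilar | 2 | 1 |
| infliximab + its biosimilar + adalimumab | >2 | 2 |
| infliximab + its biosimilar + vedolizumab | >2 | 2 |

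A child with three or more distinct molecules is at >2 either way and does not move.

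**Biologics failed.** Footnote d adds a condition, so a switch between products is not enough.

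| Infliximab history | As written | Merged |
|---|---|---|
| both products stopped for a footnote d reason | 2 | 1 |
| originator switched for a non-medical reason, biosimilar stopped for a footnote d reason | 1 | 1 |

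**Failed anti-TNFs.** Footnote c is not attached to this row, and footnote e has no merge rule. If unique means distinct molecule, a child who failed both infliximab products counts as 1. If it means distinct listed product, the child counts as 2. On that second reading a child who failed both adalimumab products would count as 2 failed anti-TNFs but only 1 failed biologic, which cannot be right. The term therefore needs a definition.

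**Effect of one affected child on a reported percentage.** Shift = 100 / n:

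- n = 30: 100 / 30 = 3.3 points
- n = 20: 100 / 20 = 5 points
- n = 10: 100 / 10 = 10 points

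The children at or below 40 kg are reported in two dose groups (Table AMBU.6.2), so the shift there is larger than 5 points. SAP Section 5.2 does not give the split.

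**How many children.** Neither document gives the share with prior infliximab, or the share who had both products. Biologic-naive children are also eligible (Protocol Section 6.1, criterion 8a). The number affected cannot be derived and may be zero.

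**The case against.** The best defence is that the SAP is silent on infliximab and does not say that the two products count separately. A sensible programmer could take the adalimumab sentence as an illustration, and the label unique on the anti-TNF row suggests that counting by molecule was intended. The footnote also ends without a full stop, unlike its neighbours, which may hint at a dropped clause. The intent is probably as the defence says. But the sentence is not worded as an example, it names one pair while the parallel pair stands in the same list, and no other text supplies the missing rule. Two programmers could reasonably produce different tables.

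The second defence is that little depends on these rows, and this stands. They are descriptive, with no inferential comparison of baseline characteristics (SAP Section 6.7) and no covariate adjustment (SAP Section 6.2). The exposed/not exposed and failed/not failed rows are the same under either count. SAP Section 6.9 also provides a separate summary of prior medications.

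Three stronger readings are tempting, and the documents do not support them:

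- **That the biologic subgroup is distorted.** The factor in Protocol Section 10.3.7.1 and SAP Section 6.14 is previous use of biologic therapy, which the protocol sets against no previous use. A child who had either infliximab product, or both, is a previous user in every case.
- **That any child switched between infliximab products is reported as having failed two.** Footnote d requires a qualifying reason for stopping each product.
- **That a sizeable share of the trial is misclassified.** Infliximab's approval status says nothing about how many of these children received both products.

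**Conclusion.** The rule is wrong as written, and the point is minor. Footnote c merges one originator and biosimilar pair and leaves out the other. Literal application puts a child with both infliximab products one category too high in the row for biologics used, unless the child is at >2 anyway. The row for biologics failed is affected only when both products were stopped for a footnote d reason. Each child who moves changes a percentage by 3.3 points in the whole trial, 5 in the 20 lighter children taken together and 10 in the 10 heavier children.

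This rests on a literal reading of the footnote and on the planned group sizes. The total effect is unknown and may be nil. Eligibility, the primary PK endpoint, the efficacy analyses and the previous-biologic-use subgroup are unaffected.

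**What to change.** Replace the adalimumab sentence in footnote c with: *An originator and its biosimilars count as one biologic for every molecule.* Apply it to both the used and the failed rows, so that a molecule counts as failed once, however many of its products were stopped for a footnote d reason. In footnote e, define unique for the failed anti-TNF row in the same way. Entries recorded as another TNF biosimilar also have no rule at present and should be assigned to their molecule where the record allows.

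The cost is a sentence in each of two footnotes and a product-to-molecule mapping in the prior-therapy program. No new data are needed. The change does not touch a principal feature of the protocol, so by the criterion in SAP Section 6.1 it needs no protocol amendment.
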